11.2 Subject Confidentiality	27
11.3 Study Modification/Discontinuation	27
12. ETHICAL CONSIDERATIONS.....	28
12.1 Risk/Benefit Assessment.....	28
12.2 Pediatric Populations.....	28
13. PUBLICATION OF RESEARCH FINDINGS	28
14. REFERENCES	29

SYNOPSIS

Study Title

Compatibility of triheptanoin (C7) with the Ketogenic Diet in Patients Diagnosed with Glucose Transporter Type 1 Deficiency (G1D)

Objectives

Primary Objectives: To explore triheptanoin (C7 oil; C7) compatibility with the ketogenic diet by evaluating EEG (for the determination of outcome EEG as defined below), and seizure rate, glycemia and ketosis in proven G1D patients receiving (both prior to enrolment and for the duration of this study) a ketogenic diet.

Secondary Objectives: N/A

Design and Outcomes

This is a single-site, open-label proof of principle exploratory trial to investigate the compatibility of C7 oil with the ketogenic diet in subjects genetically diagnosed with G1D. The primary outcome measure is change in EEG during C7 supplementation. The secondary outcome measures are: changes in seizure rate, glycemia (blood glucose levels), and ketosis (beta-hydroxybutyrate levels).

Interventions and Duration

This is an open-label, single arm proof of principle trial of orally-administered C7 in subjects diagnosed with G1D and currently receiving (i.e., prior to enrolment) a ketogenic diet. The ketogenic diet will have been previously prescribed by the patient's treating physician independently of this study and for clinical reasons (i.e., the treatment of G1D epilepsy). **Because the ketogenic diet supplies well over 50% of calories from fat, subjects, who are already tolerating over this much fat as part of their previously-prescribed ketogenic diet, will replace 45% of their daily caloric intake with C7** for 24 hours, during a 48 hour inpatient stay. During observation, subjects will have continuous EEG to monitor for any potential C7-related changes in seizure activity before, during, and after C7 ingestion. Subjects will undergo clinical evaluation and comprehensive blood work at baseline and discharge, and continuous EEG and evaluation of glucose and beta-hydroxybutyrate levels while inpatient and receiving C7. Total time of participation is 4 days.

Sample Size and Population

Fifteen subjects receiving ketogenic diet and with a known (genetically determined) G1D diagnosis will be enrolled. Subjects may be male or female, between the ages of 2.5 and 35 years 11 months old (N=5 per age group: 2.5 to 6, 7-11, and 12-35 years 11 months), and must be willing to provide assent if they are of age (age 10-17). Subjects may be English or Spanish speaking. Subjects may be currently taking anticonvulsants or other medications. Because of potential C7- supplemental dietary medium chain triglyceride interference, subjects may not have had medium chain triglyceride dietary

supplements in the past 24 hours and must agree not to consume additional supplemental medium chain triglyceride while on this trial. In practice, subjects will replace any supplemental medium chain triglyceride with any other fat that they are currently consuming.

1. STUDY OBJECTIVES

1.1. The main hypotheses tested are:

- C7 metabolism will not interfere with previously-acquired ketosis in G1D, as measured by no change in EEG from pre-C7 baseline.
- C7 metabolism will not interfere with previously-acquired ketosis in G1D, as measured by no increase in observable seizure rate and no clinically relevant changes glycemia and ketosis, as measured by random glucose levels and beta-hydroxybutyrate levels.

2. BACKGROUND

2.1. Rationale

Glucose transporter deficiency type 1 (G1D), a prototypic glycolytic defect that impairs the first step of glucose metabolism, was first described in 1991 and is caused by haploinsufficiency of the blood brain barrier and astrocyte glucose transporter (1-3). In its most common form, G1D leads to epilepsy and intellectual discapacity. Associated features include microcephaly (signifying limited brain growth) and movement incoordination (ataxia). There is no alteration of systemic carbohydrate metabolism.

Some manifestations of G1D are treatable in a significant fraction of patients: In ~2/3 of over 100 subjects that we have cared for over the years, a ketogenic diet has been efficacious for seizure control but without significantly impacting intellectual discapacity or ataxia ((4) and PI observations). Therefore, G1D is at least partially responsive to the alternative fuels generated by the diet in a fraction of patients, namely even-carbon-number fatty acids and ketone bodies (2). We currently care for over 100 G1D genetically-confirmed subjects, representing ~40% of all North American and ~10% of European subjects either reported or genotyped (often by us (5) under our NIH CETT Program for G1D) and we have elucidated the principal brain metabolic pathways in G1D (6). Although much work remains to be carried out to fully understand the biochemistry of the disorder, significant progress has been made in G1D, such that we believe that the finding of enhanced anaplerosis after administration of the C7 constituent heptanoate and related indicators of tricarboxylic acid (TCA) cycle stimulation (7) warrants the trial of anaplerotic therapy at this time in this disease. An additional sense of urgency is imposed by the potential window of opportunity that closes once the child brain matures.

Because heptanoate metabolism generates acetyl-CoA, C7 can potentially stimu-

late hepatic neoglucogenesis and this can decrease ketosis via insulin release (113). Neoglucogenesis stemming from heptanoate was observed by us after infusion of heptanoate in G1D mice (28). However, the relative amount of heptanoate infused was far greater than that used for G1D subjects. This was expected because a large quantity of labeled substrate is necessary to achieve labeling of brain intermediary metabolites in human and mouse ^{13}C NMR experiments as developed by us (27, 32, 114, 115). Thus, no significant neoglucogenesis (i.e., an increase in glycemia >10 mg/dl) is obligatorily anticipated after C7 ingestion.

Preliminary studies. One G1D subject has received C7 at 45% while on a 3.5:1 ketogenic diet without clinical or analytical consequence. Our 14 G1D subjects on a regular diet studied in the fasting state (8) exhibited a mean blood glucose of 88.5 ± 1.9 mg/dl (mean \pm SEM), which did not significantly change 30-60 min after ingestion of the base dose (35%) of C7 (87.8 ± 2.4 mg/dl). Beta- hydroxybutyrate levels were also unchanged (0.25 ± 0.10 mM in the fasting state relative to 0.23 ± 0.1 mM in the post-C7 state; mean \pm SEM). The same conclusion was reached after 10 of these subjects were tested after 3 months on C7. Thus, C7 metabolism does not appreciably interfere with glucose metabolism and related ketosis (beta-hydroxybutyrate) under a regular diet.

Fifteen subjects with G1D (five per each of three age groups) and currently receiving a ketogenic diet will participate. After baseline measurements of common blood analytes, EEG, and blood ketone body levels, subjects will be given triheptanoin dosed by individual daily caloric intake, divided in 4 daily fractionated doses.

All subjects will take triheptanoin for 24 hours (4 doses) on an inpatient basis.

This study, if the hypothesis is correct, will enable future combined or comparative studies because, for 1/3 of G1D patients, the ketogenic diet is insufficient and may be supplemented with C7 or replaced by it depending on future work, whereas, conversely, C7 may prove insufficient as first line therapy in some patients and necessitate the addition of a ketogenic diet.

2.2 Supporting Data

There is evidence of beneficial effects of C7 metabolism on the TCA cycle G1D (7). This evidence stems from work in the G1D mouse model via ^{13}C nuclear magnetic resonance (NMR) spectroscopy and mass spectrometry. Open-label treatment using triheptanoin has been pioneered by us in several disorders characterized by impaired anaplerosis (9-12), proving safe, tolerable and efficacious.

The dosing, tolerability, and safety profile of triheptanoin has been documented in other disorders (9-12). Therapeutic response is seen at approximately 35% of the daily caloric needs supplied by C7 oil, and 14 years of experience administering C7 has elicited no serious adverse events. However, side effects of mild stomach upset, nausea, and mild weight gain have been observed. Because C7 oil is a fat, it is possible that subjects will

experience changes in lipid levels, cholesterol, and triglycerides, but these changes have not been observed.

3. STUDY DESIGN

This is an open-label, proof of principle trial of C7 in subjects with G1D and currently on ketogenic diet.

Fifteen subjects with G1D receiving ketogenic diet will be enrolled. Subjects will undergo baseline and exit clinic procedures in the Neurology Outpatient Clinic located in the Children's Medical Center Ambulatory Care Pavilion. Inpatient procedures including blood draws will be completed in the Children's Medical Center Epilepsy Monitoring Unit (EMU). These facilities can accommodate both pediatric and adult patients.

Evaluation of EEG will be accomplished at the pre- and post-C7 assessments. Evaluation of random glucose and beta-hydroxybutyrate levels will be accomplished at the baseline, 4 on-treatment, and exit assessments.

4. SELECTION AND ENROLLMENT OF SUBJECTS

4.1. Inclusion Criteria

- 4.1.1. Diagnosis of glucose transporter type I deficiency (G1D), confirmed by clinical genotyping at a CLIA-certified laboratory.
- 4.1.2. Stable on ketogenic diet at 2.5:1 to 4:1 ratio (i.e., no changes in ratio will have taken place for 2 months). The initiation of a ketogenic diet is previous to -and thus is not part of- this study.
- 4.1.3. Males and females 30 months to 35 years 11 months old, inclusive.

4.2. Exclusion Criteria

- 4.2.1. Subjects with evidence of independent, unrelated metabolic and/or genetic disease.
- 4.2.2. Subjects with a chronic gastrointestinal disorder, such as irritable bowel syndrome, Crohn's disease, or colitis that could increase the subject's risk of developing diarrhea or stomach pain.
- 4.2.3. Subjects with a BMI (body mass index) greater than or equal to 30.
- 4.2.4. Subjects currently not on ketogenic diet.
- 4.2.5. Women who are pregnant or breast-feeding may not participate. Women who plan to become pregnant during the course of the study, or who are unwilling to use birth control to prevent pregnancy (including abstinence)

may not participate. Females age 10 and over will be asked to provide a serum or urine sample for a pregnancy test via dipstick. Subjects will be asked to

agree to abstinence or another form of birth control for the duration of the study.

4.2.6. Allergy/sensitivity to C7.

4.2.7. Previous use of triheptanoin less than 1 month prior to study initiation.

4.2.8. Treatment with medium chain triglycerides in the last 24 hours.

4.2.9. Subjects exhibiting signs of dementia, or diagnosed with any degenerative brain disorder (such as Alzheimer's disease) that would confound assessment of cognitive changes, in the opinion of the investigator.

4.2.10. Active drug or alcohol use or dependence that, in the opinion of the investigator, would interfere with adherence to study requirements.

4.2.11. Inability or unwillingness of subject or legal guardian/representative to give written informed consent, or assent for children age 10-17.

4.2.12. Addition of a new antiseizure drug in the previous 3 months.

4.3. Study Enrollment Procedures

4.3.1. Recruitment

[name] is the Director of the Rare Brain Disorders Clinic at UT Southwestern Medical Center and Children's Medical Center Dallas. This clinic currently provides care for approximately 100 confirmed G1D subjects from around the United States. [name] current subjects will be contacted by [name] to determine interest in participating in this research. Our experience has been that, due to the childhood manifestations of this disease, the chronic nature of symptoms, and the difficulty in finding effective treatments, these families and subjects are particularly eager for clinical trial opportunities. Our pilot study of G1D (8), which was conducted to establish the feasibility of the EEG protocol as well as providing other preliminary data, recruited 14 subjects in 15 days and had to decline as many as twice that number of interested subjects who made contact just after recruitment was complete.

In addition, [name] maintains a collaborative relationship with the Glut1 Deficiency Foundation, a community-based patient advocacy 501(c)(3) organization dedicated to supporting research in G1D. [name] is an invited speaker to their annual meeting, and the G1D Foundation has expressed its willingness to support and promote our research efforts through their community boards and newsletters.

Information regarding the trial will also be posted on the ClinicalTrials.gov and UT Southwestern websites, the latter of which includes a searchable database for current trials ongoing at UT Southwestern.

An additional recruitment tool is the web-based, patient-generated G1D patient registry. The registry is an IRB-approved, HIPAA-compliant inclusive questionnaire that captures all relevant aspects of G1D natural history and therapies. The registry, which has been accessible for 1 year now, is housed in the UT Southwestern servers that contain the medical center medical records and currently has over 100 unique enrollees.

4.3.2 Screening Log and Enrollment

We anticipate enrolling approximately 8 subjects in Year 1 and 7 subjects in Year 2. Because this study is resource intensive due to the inpatient stay, and because it will be enrolling concurrently with Protocol 1 (year 1) and Protocol 2 (year 2), enrollment at this rate will allow us to schedule around available resources of both personnel and facilities. This enrollment rate also allows for flexibility in scheduling the EMU with research patients, particularly in year 2.

A screening log will be maintained in an excel spreadsheet, documenting how subjects learned about the trial ([name], community group, clinicaltrials.gov, etc.), who referred them to the trial, the reasons for ineligibility (if applicable), and the reasons for nonparticipation of eligible subjects. The research coordinator will meet with [name] at the end of each clinic day to confirm eligible and ineligible subjects seen during the day. The research coordinator will be responsible for screening the designated secure UT Southwestern email account, contacting interested subjects, and logging which subjects qualify and which subjects do not and why.

Enrollment will open in month 1, although screening will begin prior to this month. We anticipate reaching 25% enrollment for this study in month 6, 50% enrollment in month 12, 75% enrollment in month 18, and 100% enrollment in month 24.

Recruitment will be monitored monthly. If recruitment goals fail to be met within the first 6 months of opening enrollment, the recruitment log will be analyzed to clarify the reasons for lack of enrollment, and these reasons will be addressed if possible. In our experience, this population is eager for research studies and very willing to participate, even traveling from several states away to participate in research.

If we have not met recruitment goals, we have several steps in place to improve recruitment.

1. We will utilize our G1D Registry, which includes a clause to inform registered patients about clinical research, and reach out these patients if they have not been enrolled. This process will take approximately 1-2 weeks, and we will re-evaluate recruitment, based on scheduled visits, after 4 weeks.
2. If recruitment is still lagging, or we have exhausted available patients in the registry, we will work with the Glut1 Deficiency Foundation. Per the FOA, researchers are encouraged to work with and engage patient groups. We have worked with the Glut1 Deficiency Foundation in various capacities over the past

several years and maintain an excellent working relationship with them, including making their broad patient base regularly aware of our research. The Glut1 Deficiency Foundation will send an email to members with information regarding the trial, and encourage interested families to contact us if desired. This process will take 1-2 weeks, and recruitment will be re-evaluated after 4 weeks, based on scheduled visits.

3. Finally, if we still experience a lack of patients, we will reach out to the G1D Research Consortium (G1DRC; which is not contributing support letters because the Consortium is not part of this proposal), which we have established for the broad purpose of clinical investigation and patient information. There are currently 10 U.S. institutions in the consortium, which cover virtually all densely populated areas of the U.S. The relationship with Consortium members is excellent, as, even before the Consortium was formed, members had previously referred to us a total of 36 G1D patients for specialized neurological consultation.

In addition, if enrollment is slower than anticipated, it is within the scope of this research to allow an additional 2 years to enroll (months 25-48). See Protocol Timeline below.

Protocol Timeline

	Q2-Q3 2015	Q4 2015	Q1 2016	Q2 2016	Q3 2016	Q4 2016	Q1 2017	Q2 2017	Q3 2017	Q4 2017	Q1 2018	Q2 2018	Q3 2018	Q4 2018	Q1 2019	Q2 2019	Q3 2019	Q4 2019	Q1 2020	Q2 2020	Q3 2020
Pre-Award																					
Team Assembly																					
Team Training																					
IRB Approval																					
Specific Aim 1																					
Enrollment																					
Specific Aim 2																					
Enrollment																					
6 mo Follow up																					
9 mo follow up																					
Specific Aim 3																					
Enrollment																					
Data analyses																					
Data write up																					
Publication submission																					

4.3.3. Consent and Assent Procedures

Subjects will be asked to verify basic eligibility for the trial prior to enrollment (age, diagnosis, if they currently are on dietary therapy) and to provide a copy of their current medical record at the time of enrollment, if they choose to participate. Interested subjects will be securely emailed a copy of the consent prior to their enrollment appointment. The Rare Brain Disorders Clinic maintains a dedicated email address ([contact]) for correspondence with current and prospective subjects and research participants. Interested patients may ask any questions via this email, or arrange a phone conversation to answer questions prior to traveling to Dallas for enrollment. [name] or M.D. co-investigator will consent the subjects in a private exam room. Each aspect of

the trial will be thoroughly explained to the legal guardian and subject. Time will be allowed for questions to be asked. The physician will explain that participation is voluntary, the decision not to participate does not affect the quality of their standard of care treatment with the physicians, and subjects may withdraw from the study at any time. Subjects ages 10 to 17 will be asked to provide their assent, and a legal guardian will be asked to sign the consent form. Subjects under the age of 10 are not required to sign assent. The subject's legal guardian will be asked to sign the consent form for these subjects.

Subjects and legal guardians will also have the HIPAA Authorization for Research explained to them, and again any questions will be answered. The subject's legal guardian will be asked to sign the HIPAA form.

Subjects and their legal guardians will receive a signed copy of both the consent form and the HIPAA Authorization form. One copy will be placed in the research folder, and one copy will be placed in the subject's medical record.

Potential subjects who live out of state or outside the United States will have the option to consent to the study via telephone. Subjects will be provided a copy of the informed consent document, then a telephone call will be scheduled with [name]. The process of obtaining informed consent will be conducted as outlined above. The subject will sign the consent form, then send the original copy of the informed consent to [name]. A copy of the signed form from both parties will be emailed or mailed back to the family for their records.

4.3.4. Group Assignment

This is an open-label study; there is no group assignment.

5. STUDY INTERVENTIONS

5.1. Interventions, Administration, and Duration

5.1.1. Triheptanoin: A triglyceride oil containing three odd-carbon chain-length fatty acids (i.e., a triglyceride of 7-carbon heptanoic acid). Triheptanoin will be taken 4 times (approximately every 6 hours) by mouth for one day. It is dosed 4 times per day, added to ketogenic diet meals (replacing some of the fat in each meal). Subjects will receive supplementation at 45% of daily caloric intake. The oil should be taken with meals, and will be mixed with the rest of the ketogenic diet nutrients for administration.

5.1.2. Fifteen subjects will be enrolled in a 4 day proof of principle trial of triheptanoin. Administration of triheptanoin will be done in the Children's Medical Center Dallas Epilepsy Monitoring Unit.

5.1.3. Subjects will not be required to stop other medications. Subjects will be directed to maintain their usual medications, including rescue seizure medications, as necessary for the course of the study. Subjects may have any clinical medical records transferred back to their referring physician at completion of the study.

5.1.4. Side Effects: 14 years of experience with C7 diet therapy in children and adults (including 14 G1D subjects, and a larger group of patients with fatty acid oxidation defects) has failed to reveal any significant adverse effects (9-12). However, subjects may experience mild gastrointestinal upset or stomach pain, and mild diarrhea. Both of these side effects are usually resolved by lowering the initial dose of oil by one-half and gradually titrating up to the required dose. In addition, subjects who do not follow the recommendations to reduce other fat intake in their diet may experience weight gain. Once oil is discontinued, careful monitoring of fat and calorie intake usually effectively reverses the weight gain. The data indicate no adverse effects on normal metabolism. A side effects questionnaire will be used to track any self-reported side effects. Patient safety information will be updated, if necessary, after completion of this trial.

5.2. Handling of Study Interventions

5.1.1. 5.2.1. Triheptanoin will be purchased from 1) Stepan Lipid Nutrition headquartered in Maywood, New Jersey, where the company has also a production facility. The oil is supplied in 25 kg containers under a current Material Transfer Agreement, and/or 2) CKM Corporation headquartered in Racine, Wisconsin with the production facility in Racine, Wisconsin.

5.2.2. Stepan Lipid Nutrition and/or CKM Corporation will distribute the oil to the Investigational Pharmacy Services (IPS) at Children's Medical Center. The pharmacists at the IPS will dispense the oil 4 times for each subject, during their inpatient stay.

5.3. Concomitant Interventions

5.3.1. Required Interventions: There are no additional required interventions.

5.3.2. Prohibited Interventions: Subjects are prohibited from starting or changing dietary therapy or other oil-based dietary modifications (including ketogenic diet ratio or medium chain triglyceride therapy) while on study protocol. Subjects who feel this change is necessary will be withdrawn from the study for their own protection. Because of potential C7- supplemental dietary medium chain triglyceride interference, subjects may not have had medium chain triglyceride dietary supplements in the 24 hours before study initiation and must agree not to consume additional supplemental medium chain triglyceride while on this trial. In practice, subjects will simply replace any supplemental medium chain triglyceride with any other fat that they are currently consuming.

5.3.3. Precautionary interventions: Subjects will be monitored by continuous EEG for the duration of C7 administration, and for approximately 18 hours after their last dose. If subjects experience breakthrough clinical seizures, Epilepsy Monitoring Unit physicians and nurses are trained to identify and treat these seizures. Study physicians will be contacted as soon as possible for treatment directives or, if after the event, subject status update, but in the event of an

acute epileptic crisis, staff on hand are qualified and capable of handling the event.

5.4. Adherence Assessment: All C7 is administered on an inpatient basis. There are no adherence assessments.

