9.2.1.2. Laboratory Assessments

C7 metabolism will not interfere with previously-acquired ketosis in G1D, as measured by no increase in observable seizure rate and no clinically relevant changes glycemia and ketosis, as measured by random glucose levels and beta-hydroxybutyrate levels, which will remain within the pre-enrollment clinically acceptable ranges (i.e., the new values will typically be within 2SD of previous values, using as SD the SD of the normal values as determined by the laboratory).

Subjects will experience no clinically relevant changes in observable seizures, random plasma glucose, or beta-hydroxybutyrate levels, as compared to the baseline values defined above.

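### The glucose and BHB comparator in section 9.2.1.2 may pre-date a swap from MCT to another fat, so in a recent MCT user the laboratory change may combine the swap with C7

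*Combined protocol and SAP*

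**What the plan says.** **Entry.** Section 4.2.8 excludes "Treatment with medium chain triglycerides in the last 24 hours". Section 5.3.2 repeats the limit: "subjects may not have had medium chain triglyceride dietary supplements in the 24 hours before study initiation". It then describes how users comply: "In practice, subjects will simply replace any supplemental medium chain triglyceride with any other fat that they are currently consuming". The Synopsis says the same. The only stability requirement on the diet, in 4.1.2, is that "no changes in ratio will have taken place for 2 months"; the source of the fat is not covered. Section 5.3.2 also opens with a ban: "Subjects are prohibited from starting or changing dietary therapy or other oil-based dietary modifications (including ketogenic diet ratio or medium chain triglyceride therapy", applying while the subject is on protocol.

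**Laboratory comparison.** Section 9.2.1.2 is the only place that defines it. Glucose and BHB are values "which will remain within the pre-enrollment clinically acceptable ranges", explained as meaning that "the new values will typically be within 2SD of previous values", with the SD taken from the laboratory's normal values. The go/no-go rule in 9.1 defines unaltered by normal laboratory ranges and needs at least 3 of 5 subjects in each age group. Sections 2.1 and 3 describe baseline measurements made in the study before C7. Section 9.5 plans a proportion of subjects with stable glucose and BHB and names no comparator.

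**Samples before C7.** Section 6.2.2.1 has a Day 1 chemistry draw that includes random glucose. Section 6.3.10 lists BHB in the laboratory profile, but the Day 1 cell of the glucose/BHB row in the 6.1 schedule is empty. The first scheduled BHB is on the morning of Day 2, with the first dose (6.2.2.2).

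**The concern.** The trial has one arm, so the within-subject change is the only evidence on glycemia and ketosis. A long-term MCT user can meet the 2-month ratio rule having changed fat source the day before. If that subject's previous values were obtained while still taking MCT, two dietary changes lie between the reference and the on-C7 value: the swap, then C7. The stated comparator cannot tell them apart.

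The error can go either way. A swap effect could make C7 appear to disturb ketosis or glucose. A swap effect opposite in sign to a real C7 effect could cancel it and leave the subject classed as unchanged. The protocol itself cites possible interference between C7 and supplemental MCT as the reason for the 24-hour rule, so it regards MCT status as relevant.

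**Working it through.** **1. No planned figure to reproduce.** Section 9.3 says that the sample size is not justified; 3 groups × 5 = 15 is the only arithmetic.

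**2. What the comparator measures.** Let S be the change from the previous value to the post-swap, pre-C7 value, and C the change from there to the on-C7 value.

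- Comparator in 9.2.1.2: on-C7 value minus previous value = S + C.
- In-hospital, pre-dose comparator: on-C7 value minus pre-dose value = C, plus any drift still under way.

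A subject passes 9.2.1.2 if |S + C| is within 2 SD. With C = 0, a large S alone fails the subject. With S and C of opposite sign, a C beyond 2 SD can pass. If the previous values already post-date the swap, S is near zero and the problem disappears. The documents do not say which case applies.

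**3. Timing.** Inputs: 24 h minimum (4.2.8, 5.3.2), noon admission on Day 1 (6.1), first dose on the morning of Day 2 (6.2.2.2). Assumption: first dose between 06:00 and 09:00, which is 18 to 21 h after noon on Day 1.

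- If the 24 h run to admission, minimum MCT-free time is 24 h at admission and 24 + 18 = 42 to 24 + 21 = 45 h at first dose.
- If they run to the first dose, it is 24 h at first dose and 24 − 21 = 3 to 24 − 18 = 6 h at noon on Day 1.

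The protocol does not tie study initiation to either. On both readings the in-hospital pre-dose samples follow the swap.

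**4. Do usable samples exist?** Section 3 counts a baseline, four on-treatment and an exit assessment of glucose and BHB. The 6.1 schedule shows exactly four in its dedicated row (Day 2 morning and evening, Day 3 morning and discharge). So the Day 2 morning sample appears to be counted as on-treatment, and the baseline has to come from the Day 1 draw. Glucose on Day 1 is explicit. BHB on Day 1 is supported by 3 and 6.3.10 but not shown in the schedule.

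**5. What it could do to the go rule: illustration only.** This applies only if the 9.2.1.2 comparator, rather than the normal ranges in 9.1, decides who is unaltered. Assumptions, none from the documents: each subject independently passes with probability p on C7 alone; the swap alone fails an MCT user with probability q; there are m MCT users in each group of 5. A user then passes with probability p(1 − q).

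P(go) = [P(at least 3 of 5 pass)]³.

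For p = 0.90 and m = 0, the group probability is 10(0.9³)(0.1²) + 5(0.9⁴)(0.1) + 0.9⁵ = 0.0729 + 0.3281 + 0.5905 = 0.991, and 0.991 cubed (unrounded 0.99144) is 0.975.

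| p | m | no swap effect | q = 0.1 | q = 0.3 | q = 0.5 |
|---|---|---|---|---|---|
| 0.90 | 1 | 0.975 | 0.962 | 0.936 | 0.911 |
| 0.90 | 2 | 0.975 | 0.944 | 0.856 | 0.739 |
| 0.80 | 1 | 0.836 | 0.804 | 0.742 | 0.683 |
| 0.80 | 2 | 0.836 | 0.768 | 0.618 | 0.462 |

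The table covers only the direction in which the swap mimics a C7 effect. Masking is not quantified.

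**The case against.** The best defence is that the plan is less committed to a pre-swap baseline than it looks. Section 9.2.1.2 never dates its previous values, 24 hours is a minimum, and 2.1 and 3 describe an in-study baseline. A reader might infer that the reference values were taken on MCT and that the swap is therefore charged to C7. The documents do not show that. What stands is narrower: they allow it, and no analysis text makes the in-study baseline the comparator.

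A reader might also extend the concern to the primary outcome. Section 9.2.1.1 compares EEG with a pre-C7 baseline, recorded in hospital after the swap, and 6.3.8 logs seizures from before the oil. A completed swap effect is already in that EEG baseline. Only continuing drift could reach it, and nothing in the documents shows drift.

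It is tempting to say that two misclassified MCT users would exhaust a group's allowance of two failures. That joins two references: the 3-of-5 rule in 9.1 rests on normal laboratory ranges, not on previous values. It also needs a share of MCT users that the documents do not give.

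Finally, 5.3.2 may seem to prohibit what it requires. It has a benign reading: MCT is stopped before the study starts, and nothing changes afterwards. Because study initiation is undefined, a clarification is still needed, but this is not a proven contradiction.

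**Conclusion.** The point holds in conditional form. As written, 9.2.1.2 allows a recent MCT user's glucose and BHB to be judged against values that pre-date the swap, in which case the change may combine the swap and C7 in either direction. The wider fault is that 9.2.1.2, 9.1 and the in-study baseline of 2.1 and 3 give three different references, which touches all 15 subjects whether or not they used MCT.

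The size cannot be stated. It depends on how many subjects used MCT, when their previous values were taken and what the swap does, and none of these is given. In the illustration, one MCT user per group lowers P(go) from 0.975 to between 0.962 and 0.911 (p = 0.90), and two lower it to between 0.944 and 0.739. These figures rest wholly on assumed inputs and on carrying the 9.2.1.2 comparator into the 9.1 rule. The documents do not support a claim that the effects cannot be separated: post-swap, pre-C7 glucose is already planned, and BHB probably is. The plan simply does not say to use them.

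**What to change.** - **Comparator.** In 9.2.1.2, and consistently in 9.1, name the subject's own in-hospital glucose and BHB before the first dose. State in advance whether this is the Day 1 value, the Day 2 morning value or their mean.
- **Samples.** List BHB explicitly on the Day 1 draw in the 6.1 schedule, and specify in 6.2.2.2 that the Day 2 morning sample is drawn before the oil. Align 2.1, 3 and 6.3.10.
- **Record.** At the existing nutritional assessment (6.3.7), record prior supplemental MCT use, amount and stop date.
- **Report.** Describe the laboratory results by recent MCT use. Do not reapply the 3-of-5 threshold to groups reduced by removing MCT users, because the rule is undefined there.
- **Reconcile.** The sponsor should reconcile 4.1.2, 4.2.8 and 5.3.2 on whether the swap counts as a diet change, and define study initiation. No washout length is proposed here.

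Cost: small wording changes, one schedule entry and one descriptive table, with no extra visit. No extra draw is needed if BHB is run on the Day 1 sample. Downsides: the baseline rests on one or two samples, a drift still under way after the swap is not removed, and the descriptive subgroups will be very small.
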